## Analysis Plan

### F.2 Aim 1 analyses:

*Hypothesis 1a:* As compared to the control group, clinicians randomized to the intervention will have a **greater mean number objective measures of communication quality** in encounters with both Black and White patients combined and in each race subgroup.

The goal of the primary Hypothesis (1a) is to determine the efficacy of the clinician communication coaching intervention versus usual care on an objective measure of the quality of communication from baseline to post-training. Additionally, we are interested the intervention effect within Black patients and White patients separately. The quality of communication will be assessed at both baseline encounters and post-training encounters by a summary of clinician encounter counts derived from the audio recordings. We plan to use mixed-effects models as our primary analytic strategy because they will appropriately account for the intracluster correlation of multiple patient encounters for each clinician. The mixed-effects model for Hypothesis 1a will have the following form:

$\log(\mu_{ik}) = \mu_0 + \mu_1(int) + \mu_2(premean_k) + \mu_3(clinsex_k) + \mu_4(clintype_k) + b_{0k}$ , where  $Y_{ik}$  is the number of quality communication statements for patient  $i$  in the post-period clustered within physician  $k$ , and  $Y_{ik}$  is assumed to be Poisson with mean and variance equal to  $\mu_{ik}$ . The fixed effects in the model include indicator variables intervention group (*int*), each clinician's mean number of quality communication statements per conversation prior to the intervention, and the clinician stratification variables. The random intercept,  $b_{0k}$ , is normally distributed and accounts for dependence of encounters within clinicians. PROC GLIMMIX (with the quadrature option) in SAS (SAS Inc., Cary, NC) will be used to fit the mixed-effects Poisson model and test the primary hypothesis (1a). Specifically, if  $\mu_1$  is positive and significantly different than zero, this provides evidence of greater communication quality among patients and clinicians in the intervention group as compared to the control group.

The analysis for Hypothesis 1a will also be conducted for encounters with white and black patients separately.

*Hypothesis 1b:* Black patients and White patients seen by clinicians in the intervention group will report **higher mean quality of patient-centered care** compared to patients seen by control group clinicians.

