### F.3 Aim 2 Analyses:

*Hypothesis 2a:* Racial disparities in objective measures of the quality of communication will be **lower** in encounters with clinicians in the intervention group as compared to encounters with clinicians in the control group.

*Hypothesis 2b:* Racial disparities in patients' perceptions of the quality of patient-centered care will be **lower** among those seen by clinicians in the intervention group as compared to encounters with clinicians in the control group.

A mixed-effects Poisson model will again be the primary modeling strategy for the objective communication outcome Aim 2 analyses. For this Aim, however, the model will include patientrace interaction terms and will have the following form:  $\log(\lambda_{ik}) = \lambda_0 + \lambda_1(\text{Black}_i) + \lambda_2(\text{int}_k) + \lambda_3(\text{Black}_i * \text{int}_k) + \lambda_4(\text{premean}_k) + \lambda_5(\text{clinsex}_k) + \lambda_6(\text{clintype}_k) + b_{0k}$ , where  $Y_{ijk}$  is the number of quality communication statements for patient  $i$  in the post-period clustered within physician  $k$ , and  $Y_{ik}$  is assumed to be Poisson with mean and variance equal to  $\lambda_{ik}$ . Again, the random intercept  $b_{0k}$  is normally distributed and account for dependence of encounters within clinicians. In this model,  $\text{Black}_i$  is the indicator variable for whether a patient is Black (value of 1) or White (value of 0).

Post-treatment, the Black-white mean difference among patients seen by usual care group clinicians is  $BW_{uc} = \exp(\lambda_0 + \lambda_1) - \exp(\lambda_0)$ , **this represents the racial disparity in communication quality**. The B-W mean difference among patients seen by intervention group clinicians is  $BW_{int} = \exp(\lambda_0 + \lambda_1 + \lambda_2 + \lambda_3) - \exp(\lambda_0 + \lambda_2)$ .

Hypothesis 2a will be tested by  $\lambda_5$  being significantly greater than zero, indicating a greater mean number of quality communication statements for the intervention group versus the control group for Black patients as compared to White patients (i.e., the intervention group reducing the racial disparity). The estimated incident rate ratio, p-value, and 95% confidence intervals will be calculated via estimate statements in PROC GLIMMIX.

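### The SAP's two Black-White gap formulas for Hypothesis 2a leave out the covariates and random intercept of their own log-link model, so they do not give the mean difference that the text names

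*SAP*

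**What the plan says.** The Aim 2 model in SAP F.3 is, in short, log(mean) = λ0 + λ1·Black + λ2·int + λ3·Black·int + λ4·premean + λ5·clinsex + λ6·clintype + b. SAP F.2 defines premean as "each clinician's mean number of quality communication statements per conversation prior to the intervention"; no centring is stated. The random intercept b "is normally distributed and account for dependence of encounters within clinicians".

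The SAP then states: "Post-treatment, the Black-white mean difference among patients seen by usual care group clinicians is" exp(λ0+λ1) − exp(λ0), called BW_uc here, and adds that "this represents the racial disparity in communication quality". The matching intervention-arm gap, BW_int, is exp(λ0+λ1+λ2+λ3) − exp(λ0+λ2). Neither expression contains λ4, λ5, λ6 or b. No covariate values are fixed, and nothing says that the gap is conditional on b = 0.

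On output for Hypothesis 2a the SAP says: "The estimated incident rate ratio, p-value, and 95% confidence intervals will be calculated via estimate statements in PROC GLIMMIX". It does not say that BW_uc or BW_int will be estimated or tabulated.

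**The concern.** Under a log link, every term left out of the exponent multiplies the mean. It cancels from a ratio of means but not from a difference. So exp(λ0) is not the mean count for White patients of usual-care clinicians. It is the expected count for a White patient of one particular usual-care clinician: premean 0, reference sex, reference type, b = 0. The expression and the quantity it is said to equal are different things.

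These two formulas are the SAP's only quantitative definition of the disparity that Aim 2 sets out to reduce. An analyst asked for the gap in statements per encounter would code them as printed. The gap in each arm, and the absolute reduction between arms, would then be mis-scaled. The absolute scale has some importance, because the protocol's general analysis considerations say that group differences will be judged against clinically meaningful changes in the literature.

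The point is confined to Hypothesis 2a. In the linear model for 2b, covariates that do not interact with race cancel from a difference of means.

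**Working it through.** **Inputs from the documents.** Baseline mean 1.0; between-clinician CV 0.2, 0.35, 0.5; 20 clinicians per arm; 6 post-period patients per clinician (SAP, Power and Sample Size Considerations and its table). 4 baseline patients per clinician (protocol, Design & Procedures).

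**Not in the documents, so assumed.** λ4, λ5, λ6, the variance of b, the sex and type mix, and the stability of a clinician's rate from pre to post.

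**Step 1. Reproduce the plan's own figure.** For Hypothesis 1a, solve 20 = 1 + (1.96 + 0.84)² × [(r0 + r1)/6 + CV²(r0² + r1²)]/(r1 − r0)² with r0 = 1. This gives r1 = 1.47, 1.60, 1.79 against the stated 1.5, 1.6, 1.8. The mean and CV are therefore being read as the plan uses them.

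**Step 2. The omitted factor.** Average gap ÷ formula gap = F, the average over clinicians of exp(λ4·premean + λ5·clinsex + λ6·clintype + b). The shortfall is 1 − 1/F. F is the same in both arms if the covariate mix is the same.

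**Step 3. Premean has no effect, no sex or type effect.** Only b remains. With σ² = ln(1 + CV²), F = exp(σ²/2) = √(1 + CV²) = 1.020, 1.059, 1.118. The shortfall is 1.9%, 5.6%, 10.6%.

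**Step 4. Rates fully stable from pre to post, no sex or type effect.** Simulate lognormal clinician rates with mean 1.0, take premean from 4 Poisson encounters, and regress the log rate on premean:

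| CV | λ4 | exp(λ0) | Average mean | Shortfall |
|---|---|---|---|---|
| 0.2 | 0.135 | 0.856 | 1.0 | 14% |
| 0.35 | 0.31 | 0.692 | 1.0 | 31% |
| 0.5 | 0.448 | 0.572 | 1.0 | 43% |

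Fitting the Poisson random-intercept model itself to simulated counts gives slightly smaller figures. The range over methods is 11-14%, 28-31% and 41-43%.

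**Step 5. Pre/post correlation of 0.5 on the log scale.** The intercept then lies midway between its stable value, ln(exp(λ0)), and −σ²/2:
- CV 0.2: (−0.155 − 0.020)/2 = −0.0875; exp = 0.916; shortfall about 8%.
- CV 0.35: (−0.368 − 0.058)/2 = −0.213; exp = 0.808; about 19%.
- CV 0.5: (−0.558 − 0.112)/2 = −0.335; exp = 0.715; about 28.5%.

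Model fits give 6%, 17% and 28%.

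**Step 6. Direction.** Take λ4 = 0.2 with premean at 1.0, and sex and type effects of ±0.3, each at 50% prevalence. Then F = e^0.2 × √(1 + CV²) × (1 + e^λ5)/2 × (1 + e^λ6)/2.
- CV 0.2, both −0.3: 1.221 × 1.020 × 0.870² = 0.944, so the gap is overstated by 6%.
- CV 0.5, both +0.3: 1.221 × 1.118 × 1.175² = 1.885, so it is understated by 47%.
- With λ4 = −0.2 and no sex or type effect, it is overstated by 9% (CV 0.5) to 20% (CV 0.2).

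**Step 7. How typical is the clinician described?** With mean 1.0 and 4 encounters, premean is 0 for 2.4%, 3.6% and 5.3% of clinicians at the three CVs.

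**Step 8. What does not change.** With λ0 to λ3 = 0, −0.3, 0.4, 0.2 (illustrative), the gaps are −0.259 and −0.142. Multiplying both by F = 1, 1.15 or 1.7 leaves their ratio at 0.548. The interaction rate ratio stays at e^0.2 = 1.221.

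**For scale.** An average gap of 0.25 statements per encounter (assumed) would, in the stable case of Step 4, be printed as 0.25 × 0.856 = 0.214, 0.25 × 0.692 = 0.173 and 0.25 × 0.572 = 0.143.

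**The case against.** The strongest reply is that the two gaps are explanatory. They come before the statement of the test and show what the coefficients mean. The committed output is a rate ratio with its p-value and interval, and the SAP's power section describes the effect of interest as a relative difference. A gap conditional on stated covariate values and b = 0 is also a legitimate quantity in a mixed model.

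Much of this stands. A reader might infer that the trial's reported disparity will be too small by some fixed percentage. The documents do not support that: they commit to no report of either gap, and they give no value for λ4, λ5, λ6 or the random-intercept variance. A reader might also infer that the gap must be understated. That is the expected direction if clinicians are at all consistent over time, but Step 6 shows it can reverse. Nor does the omission bias the Aim 2 test: the omitted terms cancel from the race-by-intervention rate ratio.

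The reply does not rescue the formulas. The SAP does not present them as conditional. It equates them with a mean difference among patients and calls that the racial disparity, and the model printed beside them shows that this is not so.

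The coefficient that the SAP names for the Hypothesis 2a test is a separate matter and adds no weight here.

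**Conclusion.** The formulas are wrong as written, with moderate to low severity. They define the gap for a clinician with premean 0, reference sex and type and b = 0, which is not the population gap that the sentence names.

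The size is conditional. It assumes the planning mean of 1.0, CVs of 0.2 to 0.5, 4 baseline encounters and no sex or type effect:

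| Pre/post stability of clinician rates | Understatement at CV 0.2 | Understatement at CV 0.5 |
|---|---|---|
| Fully stable | 11-14% | 41-43% |
| Correlation 0.5 | 6-8% | 28-29% |
| Premean has no effect | 0-2% | about 11% |

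Sex or type effects could shrink or reverse these figures and would make them depend on the choice of reference level. Only an absolute gap, or an absolute reduction in it, computed as the SAP defines it would be affected. The interaction rate ratio, its test and its confidence interval are not. The ratio of the two gaps is also unaffected, provided that the covariate mix is the same in both arms.

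**What to change.** Replace the two formulas with standardised gaps. For each combination of arm and race, compute the model-predicted mean at every enrolled clinician's premean, sex and type, include the factor exp(σ²/2) for the random intercept, and average. Use the same pooled set of clinicians for both arms, because averaging within each arm's 20 clinicians would carry chance imbalance into the comparison. Take Black minus White in each arm and give a delta-method or bootstrap interval. State whether these gaps will be reported.

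At minimum, centre premean, state the reference sex and type, and label the gaps as conditional on b = 0. Centring removes the premean part. In Step 4, λ0 + λ4 gives exp(−0.155 + 0.135) = 0.98 at CV 0.2 and exp(−0.558 + 0.448) = 0.90 at CV 0.5. A shortfall of roughly 2% to 11% from the random intercept remains, so the label is still needed.

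The protocol's Aim 2 section prints the same two expressions beside a different pre/post model, so it should be brought into line at the same time. The cost is two formulas and a few lines of code, with no new data.

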General considerations: All variables will be described and explored using frequency tables, means, medians, standard deviations, histograms, box plots, and trajectory plots, both overall and within clinician. The primary analyses will be conducted on an intention-to-treat basis; clinicians and patients will be analyzed in the group to which they were randomized, regardless of clinician intervention adherence, using all available data. The main conclusions drawn from this trial will be based on the pre-specified hypotheses outlined below and will be tested with two-sided p-values at the standard 0.05 level. For all study outcomes, we will interpret differences between groups over time with reference to prior literature regarding clinically meaningful changes. Results from exploratory analyses will be interpreted with appropriate consideration for their exploratory nature. Statistical analyses will be performed using the latest release SAS for Windows (Cary, NC) and R/Rstudio.

The goal of the primary Hypothesis (1a) is to determine the efficacy of the clinician communication coaching intervention versus usual care on improvement in an objective measure of the quality of communication from baseline to post-training. Additionally, we are interested the intervention effect within Black patients and White patients separately. The quality of communication will be assessed at both baseline encounters and post-training encounters by a summary of clinician-encounter counts derived from the audio recordings. We plan to use mixed-effects models as our primary analytic strategy because they will appropriately account for the intracluster correlation of multiple patient encounters for each clinician and same clinicians followed over time. The mixed-effects model for Hypothesis 1a will have the following form: $\log(\mu_{ijk}) = \mu_0 + \mu_1(post) + \mu_2(post*int_k) + \mu_3(clinrace_k) + b_{0k} + b_{1kj}$, where Y_{ijk} is the number of quality communication statements for patient i at time j clustered within physician i , and Y_{ijk} is assumed to be Poisson with mean and variance equal to μ_{ijk} . The fixed effects in the model include indicator variables for the post-treatment ($post$), intervention group (int), and clinician race ($clinrace$). The random intercepts, b_{0k} and b_{1kj} , are normally distributed and account for dependence of encounters within clinicians, both between patients and on clinicians over time. PROC GLIMMIX (with

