A mixed-effects Poisson model will again be the primary modeling strategy for the objective communication outcome Aim 2 analyses. For this Aim, however, the model will include patient-race interaction terms and will have the following form: $\log(\beta_{ijk}) = \beta_0 + \beta_1(Black_i) + \beta_2(T2) + \beta_3(T2*Black_i) + \beta_4(T2*int_k) + \beta_5(T2*Black_i*int_k) + \beta_6(race_k) + b_{0k}$ and b_{1kj} , where Y_{ijk} is the number of quality communication statements for patient i at time j clustered within physician k , and Y_{ijk} is assumed to be Poisson with mean and variance equal to β_{ijk} . Again, the random intercepts, b_{0k} and b_{1kj} , are normally distributed and account for dependence of encounters within clinicians, both between patients and on clinicians over time. In this model, $Black_i$ is the indicator variable for whether a patient is Black (value of 1) or White (value of 0).

Post-treatment, the Black-white mean difference among patients seen by usual care group clinicians is $BWuc = \exp(\beta_0 + \beta_1) - \exp(\beta_0)$, this represents the racial disparity in communication quality. The B-W

mean difference among patients seen by intervention group clinicians is $BW_{int} = \exp(\beta_0 + \beta_1 + \beta_2 + \beta_3) - \exp(\beta_0 + \beta_2)$.

Hypothesis 2a will be tested by β_5 being significantly greater than zero, indicating a greater improvement in the number of quality communication statements for the intervention group versus the control group for Black patients as compared to White patients (i.e., the intervention group reducing the racial disparity). The estimated incident rate ratio, p-value, and 95% confidence intervals will be calculated via estimate statements in PROC GLIMMIX.

A similar linear mixed-effects model (rather than a Poisson) model will be used to examine the reduction in racial disparities of quality of patient-centered care and test Hypothesis 2b. Note that in a linear model framework, the coefficients will represent differences in means rather than rate ratios.

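### The SAP tests Hypothesis 2a on λ5, which in its own model is the clinician-sex coefficient and not the race-by-intervention interaction (λ3); the protocol has the test right and the disparity formulas wrong

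*SAP*

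**What the plan says.** **SAP, F.3 Aim 2 Analyses.** The model for the post-period count has an intercept λ0, then λ1 (Black) and λ2 (intervention), and continues "\lambda_3(\text{Black}_i * \text{int}_k) + \lambda_4(\text{premean}_k) + \lambda_5(\text{clinsex}_k"), with λ6 for clinician type and a clinician random intercept. The decision rule is: "Hypothesis 2a will be tested by $\lambda_5$ being significantly greater than zero". The SAP's two disparity formulas (BWuc and BWint) use only λ0 to λ3.

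**Protocol, F.3 Aim 2 Analyses.** The model covers both periods. β1 is Black, β2 is the post-period indicator T2, β3 is T2×Black, the intervention enters through "\beta_4(T2*int_k) + \beta_5(T2*Black_i*int_k"), and β6 is clinician race. Hypothesis 2a is tested on β5. The disparities described as post-treatment are BWuc = exp(β0+β1) − exp(β0) and "BW_{int} = \exp(\beta_0 + \beta_1 + \beta_2 + \beta_3) - \exp(\beta_0 + \beta_2").

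**Hypothesis 1a.** The models differ here too. The protocol (Data Analysis & Statistical Considerations) uses both periods, with "\mu_1(post) + \mu_2(post*int_k) + \mu_3(clinrace_k) + b_{0k} + b_{1kj"}. SAP section F.2 models post-period counts only, with the clinician's pre-period mean, clinician sex and clinician type as covariates.

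**The concern.** A pre-specified decision rule should name the coefficient that carries the hypothesis. In the SAP, the subscript in the rule and the subscripts in the model disagree. λ5 would be the right label if the term order were that of the protocol model, where the fifth coefficient is the three-way interaction. The protocol's disparity formulas, in turn, have the form that suits the SAP's post-only model. The likely explanation is partial updating between two different models, although neither document says so.

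Hypothesis 2a concerns the primary outcome, and the protocol says its main conclusions rest on the pre-specified hypotheses. Followed literally, the SAP would claim or deny a reduction in racial disparity on the strength of a clinician-sex effect. The protocol formulas would report the usual-care disparity under the intervention arm's name.

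**Working it through.** **1. SAP model: which coefficient is the interaction?** Hold the pre-period mean, clinician sex, clinician type and random intercept fixed.

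- Black/White rate ratio, usual care: exp(λ1).
- Black/White rate ratio, intervention: exp(λ1+λ3).
- Log of the ratio of the two: (λ1+λ3) − λ1 = λ3.

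λ5 cancels. The SAP's own BWint = exp(λ0+λ1+λ2+λ3) − exp(λ0+λ2) also uses λ3 as the interaction, so the formulas agree with the model and the decision rule does not.

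**2. Protocol model: what do the formulas compute?** Post-period means (T2 = 1) at the reference clinician race and zero random effects:

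| | White | Black |
|---|---|---|
| Usual care | exp(β0+β2) | exp(β0+β1+β2+β3) |
| Intervention | exp(β0+β2+β4) | exp(β0+β1+β2+β3+β4+β5) |

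The expression labelled BWint is the difference across the usual-care row. The expression labelled BWuc is the gap at T2 = 0, which this model takes to be common to both arms. Neither contains β4 or β5, the only intervention terms.

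Example with assumed values β0 to β5 = 0, −0.3, 0.05, 0.02, 0.4, 0.3:

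- Labelled BWuc: exp(−0.3) − exp(0) = −0.259, the baseline gap.
- Labelled BWint: exp(−0.23) − exp(0.05) = −0.257, the usual-care post-period gap.
- Actual intervention-arm post-period gap: exp(0.47) − exp(0.45) = +0.032.

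**3. The plan's own power figures.** The SAP's detectable rate ratios for 2a are 1.8–2.2, 1.9–2.3 and 2.1–2.5 at CV 0.2, 0.35 and 0.5. The cluster-randomized Poisson formula is

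c = 1 + (z₀.₉₇₅ + z₀.₈₀)² × [(r0+r1)/y + CV²(r0²+r1²)] / (r1−r0)²,

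with c = 20 clinicians per arm, r0 = 1.0 and y = 2 or 1 patients per clinician. Solving for r1 gives 1.81, 1.92, 2.09 (y = 2) and 2.19, 2.30, 2.47 (y = 1). The SAP figures reproduce. The SAP presents them as figures for the race-by-intervention interaction, which is λ3, so they do not change.

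**4. Size of the consequence.** The λ3 contrast compares Black and White patients of the same clinician, so the clinician intercept cancels. Assume 240 post-period patients in four cells of 60 (even race mix), mean 1.0 in three cells and the interaction rate ratio R in the fourth, with no overdispersion.

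- SE(λ3) = √[(3 + 1/R)/60].
- R = 2.5: SE = √(3.4/60) = 0.238; ln 2.5 = 0.916; z = 3.85; power = Φ(3.85 − 1.96) ≈ 97%.
- R = 2.1: SE = √(3.476/60) = 0.241; ln 2.1 = 0.742; z = 3.08; power = Φ(3.08 − 1.96) ≈ 87%.

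These exceed the SAP's 80% because the SAP uses an effective sample of 60 and adds between-clinician variation.

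A simulation gave the same picture. It used 40 clinicians with 4 pre and 6 post encounters each, an assumed CV of 0.35, 1000 runs per scenario, and Poisson GEE standing in for the mixed model. The table shows the share of runs significant in the positive direction.

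| True interaction ratio | True clinician-sex ratio | λ3 test | λ5 test |
|---|---|---|---|
| 1.0 | 1.0 | 3.0% | 4.5% |
| 2.1 | 1.0 | 88.2% | 3.5% |
| 1.0 | 1.5 (assumed) | 4.0% | 80.7% |

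**The case against.** The strongest reply is that this is a labelling slip whose meaning is not in doubt. The sentence containing λ5 goes on to describe the effect "for the intervention group versus the control group for Black patients as compared to White patients (i.e., the intervention group reducing the racial disparity"), which is λ3. The SAP's BWint formula uses λ3, and its power section sizes the interaction. An analyst coding the described contrast would most likely test the right term. This stands as to intent and lowers the chance that clinician sex would actually be tested. It does not make the stated coefficient correct, and the SAP names no other coefficient for the 2a test.

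Three further points are fair:

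- Both documents call 1a the primary hypothesis, and the SAP's 1a rule is unaffected.
- The protocol's 2a test on β5 is correct, and no test is attached to its disparity formulas, so the harm there is to reported estimates.
- The documents give no clinician-sex effect, so the 80.7% is hypothetical. That an unrelated coefficient rejects at about its nominal rate is true by construction.

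A separate point is that λ3 is a ratio contrast while BWuc and BWint are absolute differences. With λ0 = 0, λ1 = −0.3, λ2 = 0.8 and λ3 = 0.1, the gap goes from −0.26 to −0.40 although λ3 is positive. Correcting the subscript does not settle that, and it is not part of this point.

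**Conclusion.** The concern holds and must be fixed. The SAP's decision rule for Hypothesis 2a names the clinician-sex coefficient; the interaction is λ3. The protocol's formula for the intervention-arm disparity is the usual-care post-period disparity, and its usual-care formula is the baseline gap common to both arms. These findings come from matching subscripts to terms and need no numerical assumption.

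The size of the effect does rest on assumptions. The hand-calculated power for λ3, about 87% at a ratio of 2.1 and 97% at 2.5, assumes an even race mix, a mean of 1.0 and no overdispersion. The simulated rates assume CV 0.35 and, in one scenario, a clinician-sex ratio of 1.5. The formulas in both documents also leave out the clinician covariates, so they hold at reference values only; this does not alter the conclusion.

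**What to change.** **SAP, F.3:** replace λ5 with λ3 in the Hypothesis 2a decision rule.

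**Protocol:** state which document's 1a and 2a models govern, then do one of the following.

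- Replace the protocol's 1a and 2a models, tested coefficients and formulas with the SAP versions.
- Keep the protocol's pre/post model and its β5 test, and correct the post-period disparities to BWuc = exp(β0+β1+β2+β3) − exp(β0+β2) and BWint = exp(β0+β1+β2+β3+β4+β5) − exp(β0+β2+β4). The SAP must then be reconciled with that model.

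The cost is wording in two documents. No data collection, sample-size or power figure changes because of this correction. It should be made and dated before outcome data are analysed by arm, so that the choice of model and coefficient is not open to question afterwards.
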